Retention plans will include weekly contact by a member of the research team to participants throughout the duration of their involvement in the study. Research staff will clearly explain the requirements of the study prior to enrollment, obtain several contact avenues (phone numbers, email), and will be flexible in scheduling appointments. Weekly assessment of participant engagement and needs will be determined to maximize retention to study completion. Reports of research results will also be made available. At this time, recruitment tools will include a flyer, email correspondence (attached below), and social media advertising on UK's CCTS and Sanders-Brown Center on Aging accounts. Should we decide to utilize additional recruitment tools, we will pursue IRB modification for each of the additional recruitment tools and advertisements

De-identified participant quotes specifically related to the utilization of the intervention may be used for advertising in the form of flyers, emails, and website posts, including social media. Participants will be invited via REDCap link to provide permission to use their deidentified quotes for this purpose. (attached).

Attachments

Attach Type	File Name
Advertising	lyer 6-24.docx
Advertising	SB-015 research match.pdf
Advertising	SB-015 social media.pdf

Advertising SB-015-flyer.pdf	
Advertising SB-015_MON.pdf	
Advertising quotes mod.docx	
Advertising Harmony at Home flyer v2_STAMPED.pdf	
Advertising SB-015b-flyer.pdf	
Advertising SB-015b_monitor.pdf	
Advertising SB-015b_researchmatch.pdf	
Advertising SB-015b_social media.pdf	

Research Procedures

Describe how the research will be conducted.

- What experience will study participants have?
- · What will study participants be expected to do?
- How long will the study last?
- Outline the schedule and timing of study procedures.
- Provide visit-by-visit listing of all procedures that will take place.
- Identify all procedures that will be carried out with each group of participants.
- Describe deception and debrief procedures if deception is involved.

Differentiate between procedures that involve standard/routine clinical care and those that will be performed specifically for this research project. List medications that are explicitly forbidden or permitted during study participation.

Use of protected health information will be used for recruitment purposes only and medical charts will not be accessed following recruitment tasks.

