Visit 2: Baseline data will be collected at Visit 2 consisting of seven surveys/questionnaires completed during the visit with the study coordinator: the Revised Memory and Behavior Problem Checklist, Adult Sensory Profile, Canadian Occupational Performance Measure, 6-Item Revised Caregiver Appraisal Scale; 6-Item Activities of Daily Living; 8-Item Instrumental Activities of Daily Living, Pearlin Mastery assessment, Stait-Trail Anxiety Scale, and Perceived Stress Scale. . The Situational Assessment Activity and Function Profile will be emailed or mailed to you for completion, as well. A focus group will also be held with selected participants. All intervention materials will be mailed to the patient's home following visit 2. Intervention materials will include items which offer environmental modifications to the home, for example:

Visit 3: The Occupational Therapist will meet with you for Visit 3. This will initiate week 1 in the behavior workbook. During this visit, the therapist will complete the Canadian Occupational Performance Measure, the Home Occupational Environment Assessment, and the Situational Assessment of the Home Environment.

Visit 4-8: At the end of each week, you and the patient you care for will meet with an occupational therapist to complete intervention training, as well as review the behavior journal and adverse events. These visits will last approximately one hour.

Visit 9: At the final week of intervention, you will engage in a two-hour session which will involve of adverse events, and completion of the Revised Memory and Behavior Problem Checklist, CES Depression scale; 6-Item Revised Caregiver Appraisal Scale; 6-Item Activities of Daily Living; 8-Item Instrumental Activities of Daily Living; Canadian Occupational Performance Measure, Stait-Trait Anxiety Scale; Zarit Caregiver Burden Scale, Pearlin Mastery assessment and Perceived Stress Scale surveys/questionnaires. A focus group will also be held with selected participants. The focus group will consist of the first ten participants willing to participate. The focus group will last approximately 60 minutes and will be conducted over zoom. The focus group will provide feedback needed to refine the intervention to specific needs of caregivers in rural Appalachia.

Visit 10: Four weeks following completion of the intervention, you will complete a follow up session consisting of the same visit 9 assessments.

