Lastly, the researcher may contact the caregivers to confirm or clarify interpretation of subjective information gained video conferences. The contact may be via phone, email, or a virtual meeting.

66767 CLOSED

All

It is anticipated that caregivers will spend approximately 11 hours on zoom as part of this study and around 45 hours in at-home intervention and documentation. Screening and baseline will take approximately 1-2 hours, visits on weeks 1-5 will total approximately 5 hours, visit for treatment week will last 2 hours and visit for follow up will task around 2 hours. We anticipate an average of one hour per day over the six week intervention to be used for intervention deliver and documentation in the behavior journal (42 hours) with additional time to complete assessments at home (approx. 3 hours) during baseline and follow up visits.

Throughout the 10 weeks of participant contact, should the participant express significant improvements related to the intervention, a permission request will be provided to assess their interest in allowing quotes related to the intervention to be used as testimonials of the intervention for recruitment and advertising purposes.

Each patient will complete the 6-week Harmony at HOME telehealth intervention: The following tasks will be associated with participation in this study and will take place at the patient's home using Zoom video conferencing. Informed consent will be obtained prior to the following research procedures.

Visit 1: Review and obtain informed consent from LAR and assess if dissent behaviors are present from patient (approximately 30 minutes)

Visit 2-7: At the end of each week, caregivers and patients will meet with an occupational therapist to complete intervention training, as well as review the behavior journal and adverse events. The patient will engage with the interventionist through discussion and dialog of behaviors, concerns, or feedback regarding intervention training information. These visits will last approximately one hour with the caregiver and patient.

Lastly, the researcher may contact the patients to confirm or clarify interpretation of subjective information gained during the Zoom video conferences. The contact may be via phone, email, or a virtual meeting.

It is anticipated that patients will spend no more than 8 hours on zoom. Approximately 15 minutes for baseline, Treatment weeks 1-6 will last around 1 hour each, and 1 hour for follow up.

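### The plan permits testimonial requests, triggered by voiced improvement, before the Visit 9 and Visit 10 self-reports, an avoidable reporting risk in an unmasked one-arm study

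*Combined protocol and SAP*

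**What the plan says.** The caregiver part of Research Procedures, after the Visit 10 description, sets a window covering all 10 weeks of contact and reads: "should the participant express significant improvements related to the intervention, a permission request will be provided to assess their interest in allowing quotes". The purpose is given as "to be used as testimonials of the intervention for recruitment and advertising purposes". What counts as a significant improvement is not defined.

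Subject Recruitment Methods & Advertising, which describes recruitment to this study, adds: "De-identified participant quotes specifically related to the utilization of the intervention may be used for advertising", and lists flyers, emails and web or social media posts as channels. On the process it says: "Participants will be invited via REDCap link to provide permission to use their deidentified quotes for this purpose".

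On outcome timing, Visit 9 is described as follows: "At the final week of intervention, you will engage in a two-hour session", with the outcome scales completed then. For Visit 10 the plan says: "Four weeks following completion of the intervention, you will complete a follow up session consisting of the same visit 9 assessments".

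Study Design gives a one-arm, pre/post study of 40 dyads. Data Collection & Research Materials names the 4-item Pearlin mastery sub-scale as primary, with burden, stress, caregiver satisfaction and behaviour problems as exploratory outcomes. The statistical analysis plan on the coversheet uses a linear mixed model to ask whether the mean differs among three visits.

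**The concern.** The request depends on what the caregiver has said about benefit, and it can come before she completes the scales that measure benefit. Someone who has just been asked to endorse a programme may answer later questions about herself in a way consistent with that endorsement. The result would look like success: mastery up, and burden, stress and behaviour-problem scores down.

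A concurrent control arm would give some basis for judging such a shift. Here change over time within one group is the only estimate of effect, no masking is described, and the analysis has no term for having been asked for a quote or having seen one. The mastery result, named as primary, is the one most exposed. Retention and adherence, which drive the sample size, are not self-rated scales. Testimonials could affect them mainly through who enrols.

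**Working it through.** **1. Timing.** The intervention lasts 6 weeks. Visit 9 falls in week 6 and Visit 10 four weeks later, at about 6 + 4 = 10 weeks. The request window is also 10 weeks of contact.

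- A request during the intervention weeks can precede every post-baseline outcome.
- A request between Visits 9 and 10 can precede the follow-up outcome.
- Weekly therapist visits and weekly staff contact give many occasions for improvement to be voiced.
- Nothing in the text delays the request until questionnaires are complete, and nothing keeps quotes from people not yet enrolled.

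**2. The plan's own figures.** There is none for this point. The only power statement concerns the adherence rate against 60% and plays no part here. The documents give no SD of change, no share of caregivers asked and no size of reporting shift.

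**3. Illustration under assumptions.** The planned mixed model is simplified to a one-sample t-test on change.

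- From the documents: n = 40 (planned sample); n = 30 (0.75 × 40, the retention target); significance level 0.05, with two-sided testing assumed because sidedness is not stated.
- Assumed: true change 0; SD of change 1; a share *f* of caregivers whose reports shift favourably by *d* SD, with *f* = 10%, 25% or 50% and *d* = 0.3 or 0.5.
- Mean shift: *b* = *f* × *d*. Noncentrality: λ = *b*√n. False-positive rate: P(|T| > t₀.₉₇₅) for a noncentral t with n − 1 degrees of freedom.

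| *f* | *d* | *b* | λ, n = 40 | rate, n = 40 | λ, n = 30 | rate, n = 30 |
|---|---|---|---|---|---|---|
| 10% | 0.3 | 0.03 | 0.19 | 5.4% | 0.16 | 5.3% |
| 10% | 0.5 | 0.05 | 0.32 | 6.1% | 0.27 | 5.8% |
| 25% | 0.3 | 0.075 | 0.47 | 7.5% | 0.41 | 6.8% |
| 25% | 0.5 | 0.125 | 0.79 | 12.0% | 0.68 | 10.2% |
| 50% | 0.3 | 0.15 | 0.95 | 15.2% | 0.82 | 12.5% |
| 50% | 0.5 | 0.25 | 1.58 | 33.8% | 1.37 | 26.3% |

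If no one's reporting shifts, the rate is 5%.

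**4. Could the data reveal it afterwards?** Suppose outcomes are compared between caregivers enrolled before and after quotes were first advertised, split 20 and 20. The 95% half-width is t₀.₉₇₅,₃₈ × √(1/20 + 1/20) = 2.024 × 0.316 = 0.64 SD. That is more than twice the largest mean shift above (0.25 SD).

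**The case against.** **The added exposure is small.** The caregiver has already voiced improvement, and the request is a REDCap link about de-identified quotes. Against weekly one-to-one therapist contact and about 45 hours of work at home, it is a minor influence. Most expectation bias comes with an unmasked one-arm pilot and would remain after the fix. This stands as a limit on the size, but the request is a separate, avoidable addition that serves no study objective.

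**Permission is not practice.** A reader might infer that caregivers were asked before their outcomes and that their quotes were used to recruit others. The documents do not show this. The window also allows requests after Visit 9 or at Visit 10, use is worded as something that may happen, and it needs the participant's permission. The permission form is listed among the attachments but its content is not available, and it might set the timing.

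**Adverts.** A reader might also infer that testimonial adverts push later caregivers' change scores in the favourable direction. That does not follow. Adverts would be seen before enrolment, and so before the Visit 2 mastery baseline. Raised expectations could move the baseline as well as the later scores. Only later enrollees who saw such material would be affected, and cohort, clinic, referral and chart-review routes also feed the study.

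**Stakes.** The aim is feasibility with a preliminary test of mechanism, and no confirmatory claim rests on the scales. That is fair, but mastery is still named as the primary outcome.

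**Conclusion.** The point holds as a risk that the plan permits and could easily avoid. The text allows an endorsement request, conditional on voiced improvement, before either post-baseline assessment. The design offers no means of separating a resulting reporting shift from an effect. The likely direction is favourable, which means higher mastery but lower burden, stress and behaviour-problem scores.

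A stronger statement, that the results are biased, is not supported. The documents record neither how many requests were made nor when, and they report no observed shift. The illustrated false-positive rates, about 5.4% to 34% with 40 caregivers and 5.3% to 26% with 30, rest wholly on the assumed shares and shifts and on a simplified test. At the low end the rate is practically nominal. The case for changing the text rests on how little the change costs.

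**What to change.** Two changes of wording:

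- **Research Procedures, caregiver section:** replace the phrase that opens the request window for the whole 10 weeks with *After all Visit 10 questionnaires are complete*.
- **Subject Recruitment Methods & Advertising:** state that participant quotes will not be used in this study's recruitment material until enrolment has closed.

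The cost is a short IRB modification, fewer or later testimonials, and no testimonial adverts during recruitment. Flyers, email, ResearchMatch, clinic referral and social media remain available.

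The file is marked closed, the anticipated end date is 7/31/2023 and the analysis plan is in the past tense, so conduct may already have ended. In that case, report whether and when quotes were requested, relative to each caregiver's Visits 9 and 10, and whether and when they were advertised, as a disclosed limitation. Any comparison of caregivers enrolled before and after first use should be descriptive only. Besides its imprecision, it is confounded with calendar time and with refinement of the intervention after the focus groups.

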Document Coversheet

Study Title: Creating Harmony at HOME: A Pilot Study of a Telehealth Based Program for Rural Caregivers' Ability to Adapt Home Environments for Adults With ADRD

Institution/Site:	University of Kentucky
Document (Approval/Update) Date:	Protocol 7/17/23
NCT Number:	NCT05202223
IRB Number	66766
Coversheet created:	10/30/23

NCT05202223: Creating Harmony at HOME: A Pilot Study of a Telehealth Based Program for Rural Caregivers' Ability to Adapt Home Environments for Adults With ADRD

Statistical analysis plan:

Analysis included mean and standard deviation of each endpoint at each visit. A linear mixed model was completed to determine if the mean response varied among the 3 visits (P value listed in the last column). Final analyses used a modified intent to treat (mITT) for a completers analysis which included those participants who completed visit 2.

-Which IRB-

Medical
 OnMedical

-Protocol Process Type-

Exemption

IMPORTANT NOTE: You will not be able to change your selections for "Which IRB" and "Protocol Process Type" after saving this section. If you select the wrong IRB or Protocol Process Type, you may need to create a new application.

See below for guidance on these options, or refer to ORI's "Getting Started" page. Please contact the Office of Research Integrity (ORI) at [contact] with any questions prior to saving your selections.

Which IRB

The Medical IRB reviews research from the Colleges of:

- Dentistry
- Health Sciences
- Medicine
- Nursing
- Pharmacy and Health Sciences
- and Public Health.

The Nonmedical IRB reviews research from the Colleges of:

- Agriculture
- Arts and Sciences
- Business and Economics
- Communication and Information
- Design; Education
- Fine Arts
- Law
- and Social Work

Note: Studies that involve administration of drugs, testing safety or effectiveness of medical devices, or invasive medical procedures must be reviewed by the **Medical IRB** regardless of the college from which the application originates.

Which Protocol Process Type

Under federal regulations, the IRB can process an application to conduct research involving human subjects in one of three ways:

- by exemption certification
- · by expedited review.
- by full review;

The investigator makes the preliminary determination of the type of review for which a study is eligible. Please refer to ORI's "Getting Started" page for more information about which activities are eligible for each type of review.

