This study will utilize a one-arm, pre/post design. Consent will be obtained electronically using REDCap survey distribution. Researchers will assess the feasibility of the primary outcome: increased caregiver competence (Pearlin mastery sub-scale on caregiver competence). Forty persons with dementia and their caregivers will be recruited for participation from the University of Kentucky Alzheimer's Disease Center (UK-ADRC), UK Telehealth Neurology Clinic, and Kentucky Neuroscience Institute. A sample of 40 caregivers has 80% power to show that the compliance (protocol adherence) rate is =60% versus the alternative that the compliance rate is <60% at the 0.05 level of significance. This sample size will allow for assessment of feasibility as the primary outcome based on retention of =75% of study participants completing the study, with =60% protocol adherence, estimated from current clinical trials at UK-ADRC and rehabilitation feasibility trials. All data will be collected remotely and stored electronically on REDCap servers approved by the University of Kentucky IRB. Statistical analyses will be completed using R and SAS programming Exploratory analyses will be conducted to gather feasibility data on the potential efficacy of with assistance from D the intervention on secondary outcomes, including behavior, functional performance, and caregiver burden, with change from baseline to the end of the study and 1-month post-intervention follow up using analysis of covariance (ANCOVA) that will include prespecified covariates (i.e., age, gender, education, disease state, comorbidities). Frequencies of demographic variables (sex, age, cognitive status, education, caregiver relationship, caregiver age), behavior change, and adverse events will be compared among participants within the same group and between groups for differences using either Fisher Exact or chi-square tests.

[figure not shown]
Intervention description:

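### The claimed 80% power to show adherence of at least 60% is not a property of the test described: that rate is the null hypothesis, and no true rate is given for the 80%

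*Combined protocol and SAP*

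**What the plan says.** The sample-size statement is in the protocol's Research Procedures section, in the paragraph that restates the one-arm pre/post design. For 40 caregivers it claims "80% power to show that the compliance (protocol adherence) rate is =60% versus the alternative that the compliance rate is <60" per cent, "at the 0.05 level of significance". The condition to be shown is thus an adherence rate printed as equal to 60%. I read the printed equals sign as a greater-or-equal sign lost in text extraction; nothing below depends on that.

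The next sentence ties the sample size to feasibility benchmarks: "retention of =75% of study participants completing the study, with =60% protocol adherence, estimated from current clinical trials at UK-ADRC and rehabilitation feasibility trials". So 60% appears both as the threshold of the test and as a rate estimated from other trials. The 75% is retention, which is a different quantity.

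The text does not name the test, its sidedness, the true adherence rate at which the 80% applies, or how adherence is classified (yes/no per caregiver, or a share of sessions). The Statistical analysis plan on the coversheet describes means, standard deviations and one model, "A linear mixed model was completed to determine if the mean response varied among the 3 visits". It has no test of adherence, so it does not supply the missing inputs.

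**The concern.** Two things are wrong with the sentence as it stands.

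- **Direction.** A significance test can give evidence for its alternative. Here the alternative is adherence below 60%, so the condition that the study is said to have power to show is the null. Failing to reject the null is not evidence that it is true, least of all with 40 observations.
- **Missing input.** Power is a function of the true rate. Without that rate, a power figure cannot be checked or interpreted. The one adherence figure in the text equals the threshold, and there the chance of rejection is only the type I error.

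This is the only power statement in the documents, and feasibility is a stated objective. A reader could take the sentence as assurance that 40 caregivers are enough to establish adequate adherence.

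**Working it through.** **Inputs from the protocol (Research Procedures).** n = 40 caregivers; threshold p0 = 0.60; significance level 0.05; stated power 80%; retention benchmark 75%.

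**Assumptions not in the documents.** Adherence is yes/no per caregiver, and the test is an exact binomial test. Sidedness is not stated, so both versions are shown: 0.05 in one tail, or 0.025 per tail.

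**Step 1: can the 80% be reproduced?** Not from stated inputs. The candidate values in the text give the following.
- True rate 0.60, testing for a rate above 60%, one-sided: power 3.5%, which is the exact type I error.
- True rate 0.75 (the retention figure, used as if it were adherence), same test: 58.4% one-sided, 44.0% two-sided.
- A plain rule of observing at least 24/40 (60%) is met with probability 57% at a true 60% and 80% at a true 65%. With a 57% pass rate at the threshold it is not a 0.05-level test, and 65% is not in the text.

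**Step 2: the test as written** (null ≥60%, alternative <60%). Reject when X ≤ c, where c is the largest value with P(X ≤ c | 40, 0.60) at or below the tail level.
- One-sided: P(X ≤ 18) = 0.039 and P(X ≤ 19) = 0.074, so c = 18 (45%).
- Two-sided: P(X ≤ 17) = 0.019 and P(X ≤ 18) = 0.039, so c = 17.

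Power at true rate p is P(X ≤ c | 40, p). Setting this to 0.80 gives p = 0.398 one-sided and p = 0.373 two-sided (normal approximation: 0.407 and 0.383). This is power to show that adherence is low.

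One-sided, the test fails to reject with probability 1 − 0.318 = 68% at a true 50%, and 1 − 0.133 = 87% at a true 55%. An observed 19/40 (47.5%) would not be rejected.

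**Step 3: the test reversed** (null ≤60%, alternative >60%). Reject when X ≥ r, where r is the smallest value with P(X ≥ r | 40, 0.60) at or below the tail level.
- One-sided: P(X ≥ 30) = 0.035 and P(X ≥ 29) = 0.071, so r = 30 (75%).
- Two-sided: P(X ≥ 31) = 0.016 and P(X ≥ 30) = 0.035, so r = 31.

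| n = 40, alternative >60% | One-sided (≥30/40) | Two-sided (≥31/40) |
|---|---|---|
| Power at true 70% | 31% | 20% |
| Power at true 75% | 58% | 44% |
| Power at true 80% | 84% | 73% |
| True rate for 80% power | 0.791 | 0.813 |

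**Step 4: sensitivity to dropout.** At 75% retention, 0.75 × 40 = 30 caregivers complete. If those not retained leave the adherence denominator, which the text does not say, the one-sided marks become ≤13/30 or ≥23/30. The true rates for 80% power become 0.376 and 0.809. If those not retained count as non-adherent, n stays 40 and Steps 2 and 3 apply.

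**Step 5: what 40 caregivers can say.** The exact (Clopper-Pearson) 95% limits for x of n are the 0.025 quantile of Beta(x, n − x + 1) and the 0.975 quantile of Beta(x + 1, n − x). For 24/40 they are 43% to 75%; for 30/40, 59% to 87%.

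**The case against.** The strongest reply is that the sentence is loose English rather than a formal hypothesis. On that reading it means showing at least 60% as against the other possibility, so the intended direction is the useful one, and 40 caregivers do give 80% power at a true rate near 79%. A related reply is that a test against low adherence is a sensible no-go check. Both readings are coherent, and this part stands: some true rate yields 80% in either direction. But each reading needs a rate that the text omits, and the two rates, about 79% and about 40%, support very different claims.

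It is also fair that the protocol lists an attached human-subjects form whose content is not reproduced. The point is therefore limited to the protocol and SAP text available.

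A reader might be tempted further, in three ways that the documents do not support:
- **That the 80% is an arithmetic error.** It cannot be shown false, because the input that would settle it is missing.
- **That the study would have declared success on a non-significant result.** No passage says so. The non-rejection figures in Step 2 describe the literal test, not a decision rule in the plan.
- **That reported results are undermined.** The Statistical analysis plan describes an analysis of endpoint means, and no inference there rests on this figure.

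**Conclusion.** The point holds as a defect in the sample-size statement. The 80% does not describe power to show adherence of at least 60%, because that condition is the null of the stated test. Nor is the figure tied to any true rate in the text.

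Its size, for 40 caregivers: the stated test reaches 80% power only where true adherence is about 40% (one-sided) or 37% (two-sided). A test for more than 60% would need about 79% or 81%. These figures rest on yes/no adherence per caregiver and an exact binomial test; if adherence is a share of sessions, they do not apply.

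Severity is minor. This is a closed one-arm pilot whose analysis is described as done, and the consequence stops at the sample-size and feasibility statement.

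**What to change.** First state how adherence is classified, its denominator (including how caregivers who are not retained are counted) and the realised number of caregivers. Then do one of the following.

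- **Preferred: withdraw the 80% power claim.** Report the adherence proportion against the 60% benchmark with an exact 95% confidence interval on the realised number, as in Step 5, and label the change a post hoc correction.
- **If a no-go check was meant:** say that the study has power to detect a rate below 60%. Give the rate detected (about 40% for 80% power, one-sided, n = 40) and state that non-rejection does not establish 60% or more. Label this post hoc too.

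I would not restate the sentence as a test for more than 60%. The analysis is already described as done, so this would introduce a hypothesis and a 30/40 mark after the fact, with power quoted at true rates that have no basis in the documents. If adherence is a share of sessions, redo the calculation for that measure.

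The cost is wording only; sample size and data collection are unchanged.
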